8.3 Endpoint Definitions

The primary endpoints of the study are:

- 1. Number of subjects that experience during the 14 days of dapagliflozin exposure:
 - a. Events of hypoglycemia
 - b. Serious adverse events
 - c. Deaths
 - d. Adverse events leading to discontinuation of study therapy
 - e. Adverse events of interest of genitourinary infection
- 2. Number of subjects with potentially clinically significant changes in vital signs during the 14 days of dapagliflozin exposure, defined as:

Marked Abnormality Criteria for Vital Signs

- Heart Rate (bpm): HR > 100 bpm and > 30 bpm above baseline, or HR < 55 bpm and > 15 bpm below baseline
- Systolic BP (mmHg): SBP > 140 mmHg and > 20 mmHg above baseline or SBP
 90 mmHg and > 20 mmHg below baseline
- Diastolic BP (mmHg): DBP > 90 mmHg and > 10 mmHg above baseline or DBP
 55 mmHg and > 10 mmHg below baseline

Orthostatic Change

- Heart Rate (bpm): Standing HR- Supine HR > 30 bpm
- Systolic BP (mmHg): Standing SBP- Supine SBP < -25 mmHg
- Diastolic BP (mmHg): Standing DBP Supine DBP < -10 mmHg

The secondary endpoints of the study are:

- Pharmacodynamic (PD) endpoint: change from baseline in mean glucose based on 7-point central laboratory glucose monitoring achieved with dapagliflozin (1 mg, 2.5 mg, 5 mg and 10 mg per day) plus insulin versus placebo plus insulin after 7 days of oral administration of double-blind treatment.
- 2. Pharmacokinetic endpoints: multiple-dose pharmacokinetic parameters of dapagliflozin and its major inactive metabolite, dapagliflozin 3-O-glucuronide, from the plasma concentration versus time data on Day 7:
 - a. Cmax Maximum observed plasma concentration
 - b. Tmax Time of maximum observed plasma concentration

- c. AUC over a dosing interval [AUC(TAU) area under the concentration-time curve in one dosing interval]
- d. Ratio of metabolite to parent AUC (corrected for molecular weight)

Other pharmacodynamic endpoints of the study are:

- 1. Change from baseline (Day -1) after 7 days of administration of double-blind treatment in:
 - a. The percent of 24-hour glucose readings obtained from continuous glucose monitoring system (CGMS) that fall within the ranges: $\leq 50 \text{ mg/dL}$, $\leq 70 \text{ mg/dL}$, 71-180 mg/dL and >180 mg/dL
 - b. Fasting Plasma Glucose (FPG)
 - c. 24-hr urinary glucose
 - d. percent inhibition of renal glucose reabsorption
 - e. Systolic blood pressure (SBP)
- 2. The percent change from baseline (Day -1) after 7 days of double-blind treatment in the following daily insulin dose quantities:
 - a. daily basal insulin dose
 - b. daily bolus insulin dose
 - c. total daily dose of insulin

Other safety endpoints of the study are:

- 1. The proportion of subjects with adverse events (not included in the primary objective) and events and marked abnormalities in clinical laboratory tests after 14 days of administration of double-blind treatment.
- 2. The change from baseline at each post-baseline time point of selected safety clinical laboratory parameters, physical measurements, vital signs and electrocardiogram data after 14 days of administration of double-blind treatment

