5 STUDY ASSESSMENTS AND PROCEDURES

5.1 Flow Chart/Time and Events Schedule

5.1.1 Flow Chart/Time and Events Schedule

Table 5.1.1:	Flow Cha	rt/Time	and E	Events	Schedu	le						
Procedure	Screen-		Inpatient							(Outpatient	
	ing*	Baseline				Dou	ıble-Blin	d Treat	ment		Follow-Up	Notes
		Day -3	Day -2	Day -1	Day 1	Day 2 to 6	Day 7	Day 8	Day 10 ^a	Day 14/ET ^b	Day 21 [°]	*Day -3 should occur within 30 days of screening visit.
ELIGIBILITY ASSESSMENT												
Subject Reports to Site	X	X							Х	Х	Х	
Obtain Informed consent	X											
Review Medical History	Х				Х							
Review Selection Criteria	X	X			X							

dapagliflozin
BMS-512148

Table 5.1.1:	Flow Cha	art/Time	and E	Events	Schedu	le								
Procedure	Screen-			Inj	patient			Outpatient						
	ing*	Baseline				Dou	ıble-Blin	d Treat	ment		Follow-Up	Notes		
		Day -3	Day -2	Day -1	Day 1	Day 2 to 6	Day 7	Day 8	Day 10 ^a	Day 14/ET ^b	Day 21 ^c	*Day -3 should occur within 30 days of screening visit.		
Review Randomization Criteria					Х									
Furlough from Clinic								Х						
GENERAL PROCEDURES														
Brief Physical Examination	X						X			Х	Х			
Complete Physical Examination		X			X									
Seated Blood Pressure and Heart Rate	X		X	X	X	Х	X	X	Х	Х	Х			
Orthostatic Blood Pressure and Heart Rate				X	X		X			Х				
ECG	Х									Х				
Height	Х													

Date:

dapagliflozin	
BMS-512148	

Table 5.1.1:	Flow Cha	art/Time	and E	Cvents	Schedu	le						
Procedure	Screen-	Inpatient								(Outpatient	
	ing*	Baseline				Dou	ıble-Blin	d Treat	ment		Follow-Up	Notes
		Day -3	Day -2	Day -1	Day 1	Day 2 to 6	Day 7	Day 8	Day 10 ^a	Day 14/ET ^b	Day 21 ^c	*Day -3 should occur within 30 days of screening visit.
Body Weight	X		Х	Х	X	Х	X	X	X	X	Х	Collect weight at screening, daily during the inpatient portion (starting day -2) and at every outpatient visit
Body Mass Index (BMI)	Х											
Review concomitant medications/procedures	X	X	X	X	X	Х	X	X	Х	Х	Х	
Contact IVR system	Х				Х					X		
Provide Dietary/exercise Counseling		X					X		Х	X		

dapagliflozin
BMS-512148

Г

Table 5.1.1:	Flow Cha	rt/Time	and E	cvents	Schedu	le								
Procedure	Screen-			Inj	patient			Outpatient						
	ing*	Baseline				Dou	ıble-Blin	d Treat	ment		Follow-Up	Notes		
		Day -3	Day -2	Day -1	Day 1	Day 2 to 6	Day 7	Day 8	Day 10 ^a	Day 14/ET ^b	Day 21 ^c	*Day -3 should occur within 30 days of screening visit.		
Dispense ePRO device (for insulin dosing and diary data) and glucose meters/supplies and provide instruction for use		X												

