BP and HR measurements must be taken consistently as indicated throughout the study. Blood pressure measurements using a calibrated mercury sphygmomanometer throughout the study are preferred. If possible, blood pressure measurements should be taken by the same person, with the same device, throughout the study.

All measurements should occur at least 10 hours after the last ingestion of caffeine, alcohol, or nicotine. Only use either the right or the left arm when measuring these parameters. At the randomization visit, it is crucial that the blood pressure measurement and heart rate be obtained prior to the first dose of blinded study medication.

Seated BP

The subject should be allowed at least 5 minutes of rest before measurement. Seated blood pressure should be measured with the subject's arm resting on a table, and with subject's back supported and feet flat on the floor.

Seated BP and HR will be determined from three replicate measurements obtained at least 1 minute apart. The average BP and HR will be determined from these 3 replicate measurements and reported in the eCRF.

Orthostatic BP

Orthostatic measurements should be obtained following completion of seated BP and heart rate and prior to administration of study medication. The subject should rest in the supine position for at least 5 minutes prior to measurement of BP and HR. Supine BP will be determined from three replicate measurements obtained at least 1 minute apart. The average BP and HR will be determined from these 3 replicate measurements and reported in the eCRF.

The subject will then stand for 2 to 3 minutes. After this time, measure the BP with the arm supported at the antecubital fossa at heart level. Standing BP and HR will be determined from 3 replicate measurements obtained at least 1 minute apart. The average

dapagliflozin	MB102072
BMS-512148	Clinical Protocol

BP and HR will be determined from these three replicate measurements and reported in the eCRF.

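### The orthostatic criteria in primary endpoint 2 have no baseline reference, so a postural change already present before dosing and unchanged on treatment counts as an on-treatment case

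*Protocol*

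**What the plan says.** Protocol section 8.3 defines primary endpoint 2 as "Number of subjects with potentially clinically significant changes in vital signs during the 14 days of dapagliflozin exposure, defined as", followed by two lists. The synopsis carries the same lists.

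- **Marked abnormality criteria.** Each heart rate, systolic and diastolic criterion joins an absolute limit to a shift from the subject's own baseline, for example "HR > 100 bpm and > 30 bpm above baseline, or HR < 55 bpm and > 15 bpm below baseline".
- **Orthostatic change.** The three criteria are "Heart Rate (bpm): Standing HR- Supine HR > 30 bpm", "Systolic BP (mmHg): Standing SBP- Supine SBP < -25 mmHg" and "Diastolic BP (mmHg): Standing DBP Supine DBP < -10 mmHg". I read the last as standing minus supine, like the other two. None mentions baseline.

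In Table 5.1.1 (section 5.1.1) the row "Orthostatic Blood Pressure and Heart Rate" is marked, by column position, at Day -1, Day 1, Day 7 and Day 14/ET. Section 5.3.8 fixes the timing within a visit: "Orthostatic measurements should be obtained following completion of seated BP and heart rate and prior to administration of study medication". Under section 4.3 the first dose is given only once the Day 1 randomization procedures are complete. The Day -1 and Day 1 orthostatic readings therefore both precede any study drug.

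**The concern.** The endpoint is presented as a count of changes during exposure, but its two lists work differently. The marked-abnormality list detects a departure from the subject's pre-treatment state. The orthostatic list detects a state, whenever it began. Standing minus supine is a change with posture within one visit; it says nothing about change since the start of treatment.

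The entry criteria do not remove the problem. The exclusions in section 3.3.2 do not name orthostatic hypotension, and section 3.4.2 allows stable ACE inhibitors and ARBs.

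At stake is how far the orthostatic counts can be read. The protocol plans no formal test, so the raw number per arm is the result. Section 8.4.3 plans to look for a dose-related trend in selected safety endpoints, and section 1.1 says the study will help inform dose selection. With about 14 subjects per arm, one or two cases that predate treatment can blur the comparison.

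**Working it through.** **1. The definition applied to an unchanged subject.** Take a systolic difference of -30 mmHg on Days -1, 7 and 14.

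- Orthostatic criterion: -30 < -25, so it is met on Days 7 and 14 and the subject is a case. The change from Day -1 is -30 - (-30) = 0.
- Seated criterion, for contrast: a systolic pressure of 150 mmHg at baseline and again on Day 7 exceeds the 140 mmHg limit, but the rise is 0, which is not above 20 mmHg. The subject is not a case.

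The two parts of the endpoint treat an unchanged subject in opposite ways. This result does not depend on how Day 1 is handled.

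**2. Day 1.** Section 5.3.8 places the reading before the dose, and section 4.3 places the first dose after the visit procedures. The endpoint window is the 14 days of exposure, which can be read to exclude a pre-dose value. Yet Day 1 sits under the double-blind treatment heading in Table 5.1.1, and no rule states that its reading is left out. For a finding seen only on Day 1, the text does not settle the matter.

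**3. The plan's own figure.** Section 8.1 gives an 80% probability of at least one event among 14 subjects at an incidence of 11 per hundred: 1 - 0.89^14 = 0.804. This reproduces, and it does not depend on the orthostatic definition. The same formula is used next.

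**4. Size.** Inputs: n = 14 per arm (section 8.1); p = proportion meeting any orthostatic criterion before treatment. The protocol gives no value for p, so 5%, 10% and 15% are assumptions. It is also assumed that every such subject is counted and that the drug has no effect.

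- Expected pre-existing cases per arm = 14p.
- Probability of at least one in an arm = 1 - (1 - p)^14.
- Probability that a given active arm and placebo differ by two or more subjects = the sum of Bin(a; 14, p) × Bin(b; 14, p) over all a, b with |a - b| ≥ 2.

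| p (assumed) | Expected per arm | P(at least one) | P(arms differ by ≥ 2) |
|---|---|---|---|
| 5% | 0.7 | 1 - 0.95^14 = 51% | 17% |
| 10% | 1.4 | 1 - 0.90^14 = 77% | 33% |
| 15% | 2.1 | 1 - 0.85^14 = 90% | 42% |

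The expected number is the same in every arm. It cancels from a difference between arms in expectation, pulls a ratio towards one, and adds variance to both.

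**The case against.** **The orthostatic difference is already a within-subject change.** The supine value is its reference, it has its own subheading, and counting everyone who reaches a fixed postural threshold on treatment, against placebo, is a coherent safety screen. That stands as a description of a screen. It does not fit an endpoint introduced as changes during exposure, whose neighbouring criteria all require a shift from baseline.

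**The statistical analysis plan may deal with it.** Choice of baseline record, visit windows and tables often belong there, and that plan is not at hand. But the protocol wrote the thresholds out as the definition of a primary endpoint. A baseline condition added later would change that definition, not fill a gap in it.

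**The consequence is limited.** Placebo is concurrent and randomized, nothing is tested, and chance imbalance affects every count in a pilot of this size. The prevalence is assumed, and the ban on diuretics (section 3.4.1.1) and investigator discretion over risky conditions (section 3.3.2) may lower it. All of this stands, and it limits the severity.

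**A crude remedy would do harm.** Dropping everyone who met a criterion before dosing would lose a subject whose drop went from 26 to 45 mmHg, and a met/not-met table would show no shift. This stands and shapes the fix.

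**Stronger readings.** A reader might infer three further things that the documents do not support:

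- That the pre-dose Day 1 reading is counted as on-treatment. No passage says so, and the reference to exposure can be read the other way.
- That pre-existing cases are as large as any plausible drug effect. The protocol gives no expected orthostatic rate or effect.
- That the count is biased for or against dapagliflozin. Randomization spreads pre-existing cases evenly in expectation.

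**Conclusion.** The point holds for orthostatic findings that are present before the first dose and unchanged on Day 7 or Day 14/ET: as written, section 8.3 and the synopsis count them as changes during exposure. This follows from the text alone. The status of the pre-dose Day 1 reading is an ambiguity, not a stated error.

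The size rests on an assumed pre-treatment prevalence. At 5% to 15%, with all such subjects counted, each arm of 14 carries 0.7 to 2.1 pre-existing cases on average. The effect is noise and dilution in a descriptive comparison. Because no test is planned and the error has no direction, this is a should-fix. It is worth doing because the endpoint is primary and the readings needed are already scheduled.

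**What to change.** In section 8.3 and the synopsis:

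1. State that the Day -1 and pre-dose Day 1 orthostatic readings are pre-treatment and lie outside the exposure window.
2. Count an orthostatic case only if the criterion is met after the first dose (Day 7 or Day 14/ET) and the finding is new, or worse than the pre-treatment value by an amount fixed in advance. State how the two pre-treatment readings are combined into that value.
3. Show all on-treatment threshold cases, split by pre-treatment status, in a shift table by arm with the actual standing-minus-supine values, so that worsening in subjects who already met a criterion stays visible.

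The cost is a slightly more complex definition and one extra table. No new visit or measurement is needed.

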8.4 Analyses

Analyses of the data from the 14 days double-blind treatment period will be performed after all subjects have completed or have been discontinued from the study. In addition,

dapagliflozin	MB102072
BMS-512148	Clinical Protocol

all relevant queries must be resolved and the database must be locked for this 14 days period prior to the analyses.

8.4.1 Demographics and Baseline Characteristics

Frequency distributions and summary statistics for demographic and baseline variables summarized in pharmacodynamic analyses, will be computed by treatment group as well as for all subjects combined. No statistical test will be carried out for comparison of any baseline measurement among the treatment groups.

8.4.2 Efficacy Analyses

Not applicable

8.4.3 Safety Analyses

The incidence of adverse events and of marked abnormalities in clinical laboratory tests will be summarized by treatment group. All adverse events that are serious or that result in discontinuation of study therapy will be described in depth. Changes from baseline at each of the scheduled time points in each clinical laboratory parameter of interest will be summarized by treatment group. The existence of a dose related trend pattern will be assessed for selected safety and tolerability endpoints.

8.4.4 Pharmacokinetic Analyses

Summary statistics will be tabulated for Cmax, Tmax, AUC (TAU), and Ratio of metabolite to parent AUC by arm and study day for both dapagliflozin and its major inactive metabolite, dapagliflozin 3-O-glucuronide.

Geometric means and coefficients of variation will be presented for Cmax, AUC (TAU), and Ratio of metabolite to parent AUC. Medians and ranges will be presented for Tmax.

8.4.5 Pharmacodynamic Analyses

Unless otherwise specified, for all changes (or percent changes) from baseline to a specific time point post-baseline as well as for glycemic response definitions, analyses will be based on measurements available at that time point or the last post-baseline measurement prior to the time-point, if no measurement is available at that time point, ie, last observation carried forward (LOCF). For the endpoints in the inpatient period, only inpatient measures will be considered.

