4.3 Selection and Timing of Dose for Each Subject

Upon entry into the double-blind treatment period (day 1), after **ALL** randomization visit procedures have been completed, each subject will be provided 1 kit of blinded study medication containing 3 bottles (each containing 20 tablets, corresponding to the dapagliflozin/matching placebo tablets as per Table 4.1) and will take 1 tablet from each bottle every day with the morning meal, for the duration of the treatment period.

Dose titration of double-blind study medication is not permitted at any time during the study.

Guidance for insulin is provided in section 5.

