7-point central laboratory glucose monitoring (before and 2-hr after each meal [breakfast, lunch, dinner] as well as bedtime[~11 pm])				X	X		X							

dapagliflozin	
BMS-512148	

Table 5.1.1:	Flow Cha	rt/Time	and E	Events	Schedu	le						
Procedure	Screen-		In	patient			Outpatient					
	ing*	В	aseline			Dou	ıble-Blin	d Treat	ment		Follow-Up	Notes
		Day -3	Day -2	Day -1	Day 1	Day 2 to 6	Day 7	Day 8	Day 10 ^a	Day 14/ET ^b	Day 21 ^c	*Day -3 should occur within 30 days of screening visit.
FPG	X			X	Х		Х			X		
Fasting C-peptide	X											
Serum Insulin							Х					Day 7 Pre-dose, after lunch and after dinner
A1C	X											
Hepatitis Screen Panel/TSH	Х											
Fasting Serum Lipids	X						X			X		
FFA	X				X		X			X		
Serum β-hydroxybutyrate			X		X		X			X	X	

Date:

dapagliflozin
BMS-512148

Table 5.1.1:	Table 5.1.1:Flow Chart/Time and Events Schedule											
Procedure	Screen-	Inpatient					Outpatient					
	ing*	B	Baseline			Do	uble-Blin	d Treat	ment		Follow-Up	Notes
		Day -3	Day -2	Day -1	Day 1	Day 2 to 6	Day 7	Day 8	Day 10 ^a	Day 14/ET ^b	Day 21 ^c	*Day -3 should occur within 30 days of screening visit.
PK sample collection at 0 h 0.5,1,2,3,4,6,8,12, and 24 h post-dose							X	X				24 h post-dose PK sample occurs Day 8 for dose administered on Day 7.
DRUG DISPENSING												
Dispense Study Medication					X	X	X	X	X			The kit assigned to each subject on Day 1 for inpatient dosing will be the same kit each subject takes home on Day 8 for outpatient dosing.

dapagliflo	zin
BMS-512	148

Table 5.1.1:	Flow Cha	rt/Time	and E	Events	Schedu	le						
Procedure Screen- Ir				Inj	patient	atient Outpatient						
	ing*	B	aseline			Dou	uble-Blin	d Treat	ment		Follow-Up	Notes
		Day -3	Day -2	Day -1	Day 1	Day 2 to 6	Day 7	Day 8	Day 10 ^a	Day 14/ET ^b	Day 21 [°]	*Day -3 should occur within 30 days of screening visit.
Review Study Medication Compliance						Х	X	X	X	X		Subjects will be instructed to take 1 tablet from each of 3 bottles every day of the 14-day treatment period (including days 9 and 11-14).

^a Visit may be scheduled ± 1 day to allow flexibility of scheduling.

^b All subjects who discontinue should have day 14/early termination (ET) procedures as indicated here.IVRS should be called to record status (ie discontinuation). The Day 14/ET e CRF will need to be completed. The investigator should arrange appropriate follow-up care, as applicable. It is important for Day 14 to occur 14 days relative to/from first dose

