An additional secondary endpoint, related to pharmacodynamics, is the change from baseline to Day 7 in mean glucose based on 7-point central laboratory glucose monitoring, which will be summarized for each study arm. Also, the difference between each dapagliflozin dose (1 mg, 2.5 mg, 5 mg and 10 mg per day) plus insulin versus placebo plus insulin will be summarized. Assuming a common standard deviation of 30 mg/dL in each treatment group, with 14 subjects per group, the half-width of the 95% confidence interval for the difference between any dapagliflozin + insulin treatment group and the placebo + insulin treatment group is estimated to be 22.22 mg/dL.

8.2 **Populations for Analyses**

- The pharmacodynamic dataset is the Randomized Subjects dataset which is defined as all randomized subjects who receive at least one dose of double-blind study medication. Whenever using the Randomized Subjects dataset, subjects will be presented in the treatment group to which they were randomized at the start of the double-blind treatment period (even if the treatment they received was different). In addition, randomized subjects must have both a baseline and at least one post-baseline measurement for the time point under consideration to be included in the pharmacodynamic analysis of change or percent change from baseline. All efficacy analyses will be performed using the pharmacodynamic dataset.
- The safety data set is the Treated Subjects dataset which is defined as all treated subjects who received at least one dose of study medication. The Treated Subjects Data Set consists of all subjects who received at least one dose of double-blind study medication during the double-blind treatment period. The Treated Subjects Data Set would include any subject who accidentally received double-blind study medication but was not randomized in the study. All analyses using the Treated Subject Data Set will be presented by randomized treatment group, except in cases where information was available which indicated that a subject received a different treatment for the entire course of their participation in the study (or period).In this case, the safety data for those subjects will be presented by the treatment actually received. In case a subject never received the treatment as assigned by randomization, then the safety data for that subject will be presented by the first treatment received. All safety analyses will be performed using the safety data set.

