- 24 -hour urine collection Urine will be collected over a 24-hour period on days -1, 1 and 7 for assessment of glucose, sodium, uric acid and creatinine. In the morning, on the day that the 24-h urine collection is started, the first morning void is not included in the 24-h collection. The date and time of the first urine should be recorded on the urine collection log as the start of the 24-h urine collection. All subsequent urinations throughout the entire day and night, and into the following day should be collected. The first voided urine of the subsequent day should be included in the 24-hr urine collection. The urine collection ends after 24 hrs and the stop time should equal the start time of the previous day. The stop date and time should be recorded on the urine collection log.

Enrollment-Specific Safety Panel

- Hepatitis Screen Panel:
 - Anti-hepatitis C virus antibody
 - *Reflex Testing: If positive, a reflex RIBA HCV will be obtained*
- Hepatitis B surface antigen
- TSH (uIU/mL, mIU/L)
- *Reflex Testing: Abnormal TSH value at enrollment will be further evaluated by free T4 (ng/dL, pmol/L).*

Specialized Liver Panel

For subjects who are being monitored frequently as a result of confirmed AST and/or ALT > 3X ULN, additional central laboratory tests will be performed within 3 days of receipt of confirmatory results. These laboratory tests will study the possible causes of the increased ALT and/or AST and/or TB, and may include, but are not limited, to the following tests:

- Hepatitis A IgM
- Hepatitis BsAg
- Hepatitis B Core Ab IgM
- Hepatitis C virus RNA
- Hepatitis C Ab
- Hepatitis E IgM
- Epstein-Barr Virus (EBV) IgM Ab
- Lactate Dehydrogenase (LDH)
- Gamma-glutamyl-transpeptidase (GGT)
- Carbohydrate deficient transferrin (CDT)
- Prothrombin time (PT/INR)
- Iron Panel iron, ferritin, total iron binding capacity (TIBC)
- Immunology Panel including Antinuclear Antibody (ANA), Anti-Smooth Muscle Antibody (SMA) and Anti-Liver/Kidney Microsomal Antibody (Anti-LKM)
- Anti-tissue Transglutaminase Antibody

Liver Discontinuation Panel

For subjects who are discontinued from the study as a result of sustained elevated liver safety abnormalities, additional central laboratory tests will be performed at the time of Early Termination (Day 14/ET) visit. Similar to the Specialized Liver Panel, these laboratory tests will study the possible causes of the increased ALT and/or AST and/or TB, and may include, but are not limited to, the following tests:

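### LOCF for three Day 7 pharmacodynamic endpoints falls back on Day 1: a pre-dose value for FPG, a single-dose value for 7-point glucose and 24-hour urinary glucose

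*Protocol*

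**What the plan says.** - **Imputation rule (Section 8.4.5).** Changes and percent changes from baseline use the value from the scheduled assessment "or the last post-baseline measurement prior to the time-point, if no measurement is available at that time point, ie, last observation carried forward (LOCF". The rule goes on: "For the endpoints in the inpatient period, only inpatient measures will be considered". It yields to anything specified elsewhere, but Sections 8.4.5.1 and 8.4.5.2 specify nothing different.
- **Baseline (Section 8.3).** The other pharmacodynamic endpoints, including FPG and 24-hour urinary glucose, are headed "Change from baseline (Day -1) after 7 days of administration of double-blind treatment in". The secondary endpoint, 7-point mean glucose, refers to baseline without naming the day.
- **Schedule (Table 5.1.1, Appendix 2).** The profile is defined as "7-point central laboratory glucose monitoring (before and 2-hr after each meal [breakfast, lunch, dinner] as well as bedtime[~11 pm" and is marked on Days -1, 1 and 7. For the urine collection: "Urine will be collected over a 24-hour period on days -1, 1 and 7". FPG is marked at screening and on Days -1, 1, 7 and 14/ET. None of the three is scheduled on Days 2 to 6.
- **Dosing and sampling.** Under Section 4.3 the kit is provided on Day 1 once all randomization-visit procedures are done, and the subject "will take 1 tablet from each bottle every day with the morning meal". Appendix 2 requires clinical laboratory samples to be taken in the morning after a fast of at least 8 hours.
- **Inclusion (Section 8.2).** For an analysis of change, "randomized subjects must have both a baseline and at least one post-baseline measurement for the time point under consideration to be included".

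**The concern.** Carrying a value forward is defensible only if that value says something about the effect being estimated. Here the rule asks only that it be post-baseline, not that it follow any dose. With FPG baseline at Day -1, a Day 1 sample taken before the first tablet meets the condition although it can contain no drug effect. For 7-point glucose and urinary glucose, the only available Day 1 value reflects one dose and would be reported as the effect of seven.

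The missing values need not be a random subset. Section 3.5.1 makes hypoglycemia a ground for stopping study drug, so a subject stopped between Days 2 and 6 may be one whose glucose fell most, and would be represented by a value from before or just after the first dose. The expected consequence is an effect pulled toward zero in the affected arm. That matters because Section 8.4.5.1 assesses a dose-related trend with about 14 subjects per arm, and Section 1.1 says the study will help inform dose selection for later T1DM studies.

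Sections 8.2 and 8.4.5 can also be read as giving different analysis sets for the same endpoint.

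**Working it through.** **1. The plan's own figure.** Section 8.1 assumes SD 30 mg/dL and 14 subjects per arm for 7-point mean glucose. Half-width = 1.96 × 30 × √(2/14) = 22.22 mg/dL, which matches the stated figure. Nothing below changes it.

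**2. What a missing Day 7 value is filled with.**

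| Endpoint | Inpatient days before Day 7 | Carried value | Drug exposure in that value |
|---|---|---|---|
| FPG | -1, 1 | Day 1 (or an inpatient ET sample) | None |
| 7-point glucose | -1, 1 | Day 1 | 1 sample before breakfast, 6 after the meal taken with the first dose |
| 24-h urinary glucose | -1, 1 | Day 1 | Starts that morning after the first void and runs into the next day, so mostly after the first dose |
| Seated SBP | daily from Day -2 | Day 6 | On treatment |

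The FPG entry is an inference: a fasted morning sample, and a tablet taken with the morning meal after the randomization procedures. The protocol does not state outright that Day 1 FPG is pre-dose, but those instructions leave no other natural order.

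**3. Size, as an illustration.** The protocol gives no missing-data rate, so the number filled is an assumption. Let m be the active-arm subjects out of 14 filled from Day 1, and r the Day 1 effect as a share of the Day 7 effect. If filled subjects would otherwise have shown the arm's average effect, and drift common to the arms is ignored,

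share of effect retained = 1 − (m/14) × (1 − r).

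For FPG r = 0. For the other two endpoints r = 0.5 to 0.75 is an assumed range.

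| m | FPG, r = 0 | r = 0.5 | r = 0.75 |
|---|---|---|---|
| 1 | 93% | 96% | 98% |
| 2 | 86% | 93% | 96% |
| 3 | 79% | 89% | 95% |
| 4 | 71% | 86% | 93% |

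Per filled subject the loss is 1/14 = 7.1% for FPG. For the others it is 0.5/14 = 3.6% at r = 0.5 and 0.25/14 = 1.8% at r = 0.75.

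**4. Precision with observed values only.** With m missing in each of the two arms compared, the 7-point glucose half-width is 1.96 × 30 × √(2/(14 − m)): 23.06, 24.00, 25.07 and 26.30 mg/dL for m = 1, 2, 3 and 4.

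**5. Section 8.2 against Section 8.4.5.** If a measurement for the time point means one taken on Day 7, every subject LOCF would fill is already excluded and the rule has nothing to act on. If a carried value counts, the subject stays in. The two readings give a different N whenever a Day 7 value is missing.

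**The case against.** Several points on the other side stand.

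- **Not all the carried values are untreated.** A reader might infer that untreated data are analysed as the 7-day effect for all three endpoints. That fits FPG only; the Day 1 profile and urine collection mostly follow the first dose.
- **Blood pressure is not affected.** Section 5.3.8 does say "At the randomization visit, it is crucial that the blood pressure measurement and heart rate be obtained prior to the first dose", and a reader might add SBP to the list. Table 5.1.1 schedules seated blood pressure on Days 2 to 6, so SBP would carry an on-treatment value.
- **The ET visit can help.** FPG is among the Day 14/ET procedures required of subjects who discontinue. If these are done while the subject is still an inpatient before Day 7, that FPG would be carried instead of Day 1. It does not help when a Day 7 sample is simply missed or the ET visit follows discharge. The ET visit includes neither the 7-point profile nor the 24-hour urine collection.
- **Section 8.2 need not contradict 8.4.5.** The looser reading is available, so this is an ambiguity.
- **Day 7 falls within a supervised inpatient stay**, so few values may be missing, and the study is exploratory with no formal tests.
- **Spread.** A reader might infer that LOCF here understates variability. The documents do not show it; mixing subjects with no effect and full effect can widen the spread.

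It can also be said that the definition of post-baseline belongs in the SAP, and that Day -1 is not attached to the 7-point endpoint. But the carry-forward rule is fixed in the protocol without a dosing condition, Day -1 is stated as baseline for FPG, and Day -1 is the only 7-point profile scheduled before treatment.

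**Conclusion.** The point holds for FPG, 7-point glucose and 24-hour urinary glucose. As written, Section 8.4.5 replaces a missing Day 7 value with Day 1, except where an inpatient ET FPG exists. For FPG that is an untreated value, on the inference that Day 1 FPG is drawn before the first tablet; for the other two it is a single-dose value. The illustrated loss per filled subject in an arm of 14 is about 7% of the FPG effect and about 2-4% for the others. This rests on an assumed number of missing values, an assumed Day 1 share of 50-75% for the non-FPG endpoints, and filled subjects being average responders. If they respond more than average, the loss is larger. The actual bias cannot be sized from the protocol. If no Day 7 value is missing, it is zero. The Section 8.2 wording needs reconciling but is not an unavoidable contradiction. No figure stated in the protocol changes.

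**What to change.** 1. In Section 8.4.5, analyse observed Day 7 values for FPG, 7-point glucose and 24-hour urinary glucose, with no carry-forward from Day 1.
2. State that no pre-dose Day 1 value counts as post-baseline.
3. Reword the Section 8.2 inclusion condition so that it gives the same analysis set as Section 8.4.5.

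A repeated-measures model, or a baseline averaged over Day -1 and pre-dose Day 1, would be optional; neither is needed to remove the problem.

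The cost is wording only, with no new data or visits. N may fall slightly where a Day 7 value is missing. For 7-point glucose with one subject missing per arm, the CI half-width rises by 23.06 − 22.22 = 0.84 mg/dL. Observed-value analysis does not remove bias from informative dropout; it only stops pre-dose and single-dose values from being presented as 7-day values.
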